APPENDIX 4: TOXICITY SCALES FOR LABORATORY ABNORMALITIES		

19 JAN 16 Final Version 1.0	Confidential	Page 5 of 59
(SERUM CLINICAL CHEMISTRY).....		57
APPENDIX 5: TOXICITY SCALES FOR LABORATORY ABNORMALITIES (HEMATOLOGY).....		58
APPENDIX 6: TOXICITY SCALES FOR LABORATORY ABNORMALITIES (URINE)	59	

LIST OF ABBREVIATIONS

AE	Adverse Event
AESI	Adverse Events of Special Interest
ANCOVA	Analysis of Covariance
ANOVA	Analysis of Variance
BMI	Body Mass Index
CBER	Center for Biologics Evaluation and Research
CI	Confidence Interval
CRF	Case Report Form
CSR	Clinical Study Report
DMC	Data Monitoring Committee
ELISA	Enzyme Linked Immunosorbent Assay
ER	Emergency room
EXC	Excluded from analysis set
FAS	Full Analysis Set
GMC	Geometric Mean Concentration
GMR	Geometric Mean Ratio
GMT	Geometric Mean Titer
HI	Hemagglutination Inhibition
hSBA	Human complement serum bactericidal assay
ICH	International Conference on Harmonisation

19 JAN 16 Final Version 1.0	Confidential	Page 6 of 59
IM	Intramuscular	
LLQ	Lower limit of quantification	
MAR	Missing at Random	
MCAR	Missing Completely At Random	
MedDRA	Medical Dictionary for Regulatory Activities	
mg	Milligram	
mL	Milliliter	
NOCD	New onset of chronic disease	
PD	Protocol Deviation	
PPS	Per Protocol Set	
PT	Preferred Term	
SAE	Serious Adverse Event	
SAP	Statistical Analysis Plan	
SD	Standard Deviation	
SUSAR	Suspected Unexpected Serious Adverse Reactions	
TFL	Tables, Figures and Listings	
TOC	Table of Contents	
WHO	World Health Organization	
µg	Microgram	

1. BACKGROUND AND RATIONALE

The aim of this study is to assess the safety of Aluminium Hydroxide/LHD153R adjuvanted MenC-CRM₁₉₇ conjugate vaccine (MenC-CRM₁₉₇/Aluminium Hydroxide/LHD153R) and to compare the antibody-mediated immune response elicited by MenC-CRM₁₉₇/Aluminium Hydroxide/LHD153R with the licensed aluminium hydroxide adjuvanted Meningococcal C-CRM₁₉₇ Conjugate Vaccine (Menjugate®).

For further details, refer to [section 1.0 of the protocol](#).

2. OBJECTIVES

2.1 Primary Objectives

Primary Safety Objective

To assess the safety of MenC-CRM197/Aluminium Hydroxide/LHD153R as compared to that of aluminium hydroxide adjuvanted Meningococcal C-CRM197 Conjugate Vaccine.

Primary Immunogenicity Objective

To compare the antibody responses of MenC-CRM197/Aluminium Hydroxide/LHD153R and aluminium hydroxide adjuvanted Meningococcal C-CRM197 Conjugate Vaccine at Day 29, as measured by human complement serum bactericidal assay (hSBA) directed against MenC.

2.2 Secondary Objectives

Secondary Immunogenicity Objective(s)

1. To compare the antibody responses of MenC-CRM₁₉₇/Aluminium Hydroxide/LHD153R and aluminium hydroxide adjuvanted Meningococcal CCRM₁₉₇ Conjugate Vaccine at Day 8 and Day 181 after vaccination, as measured by hSBA directed against MenC. Baseline antibody titers will also be measured by hSBA.
2. To compare the antibody responses of MenC-CRM₁₉₇/Aluminium Hydroxide/LHD153R and aluminium hydroxide adjuvanted Meningococcal CCRM₁₉₇ Conjugate Vaccine, at Day 8, Day 29 and Day 181 after vaccination, as measured by an enzyme-linked immunosorbent assay (ELISA) to MenC. Baseline antibody concentrations will also be measured by ELISA.

2.3 Exploratory Objectives

1. To evaluate the systemic exposure of LHD153 at several early time-points after IM injection of MenC-CRM₁₉₇/Aluminium Hydroxide/LHD153R or Meningococcal CCRM₁₉₇ Conjugate Vaccine.
2. To explore the frequency of B cells specific for MenC polysaccharide and CRM₁₉₇ protein at baseline (Day 1) and at Day 8, Day 29 and Day 181 after vaccination with MenC-CRM₁₉₇/Aluminium Hydroxide/LHD153R or the aluminium hydroxide adjuvanted Meningococcal C-CRM₁₉₇ Conjugate Vaccine. Subsequently, the B cell

repertoire of the antigen specific B cells will be analyzed in a selected subset of subjects.

3. To explore the baseline T cell mediated immunity to CRM₁₉₇ and to evaluate the frequency and quality of CRM₁₉₇ specific T cells induced by MenCCRM₁₉₇/Aluminium Hydroxide/LHD153R compared to aluminium hydroxide adjuvanted Meningococcal C-CRM₁₉₇ Conjugate Vaccine at Day 8 and Day 29.
4. To evaluate biomarkers that may be predictive for safety and/or innate immune activation.

3. STUDY DESIGN

This is a Phase 1, randomized, observer blind, active-controlled, adjuvant dosage escalation study performed at a single center. In total, approximately 80 healthy adults (18-45 years of age) will be enrolled in the study.

Tables 1 and 2 describe the different enrollment groups, cohorts, vaccine formulations as well as the injection schedule and the enrollment stages based on Data Monitoring Committee (DMC) reviews.

Table 1. Subjects Randomized per Cohort and Treatment Dose Group

Cohort	Group	Subjects/ Group	MenC Dosage* (μ g)	Adjuvant Dosages		Total Volume/Dose	Total Subjects/Group
				Aluminium Hydroxide (mg)	LHD153R (μ g)		
1	A	4	10	1	0	0.5 mL	20
	B	16	10	1	12.5	0.5 mL	
2	A	4	10	1	0	0.5 mL	20
	C	16	10	1	25	0.5 mL	
3	A	4	10	1	0	0.5 mL	20
	D	16	10	1	50	0.5 mL	
4	A	4	10	1	0	0.5 mL	20
	E	16	10	1	100	0.5 mL	

*Conjugated to 12.5-25 μ g CRM₁₉₇

All cohorts will have a staggered entry. For each cohort, the first 5 subjects (i.e. the first 1:4 randomization block) to receive either aluminium hydroxide adjuvanted Meningococcal C-CRM₁₉₇ Conjugate Vaccine (n=1) or MenC-CRM₁₉₇/Aluminium Hydroxide/LHD153R (n=4) will be vaccinated at rate of 1 subject each day.

After entry of the first 5 subjects in each cohort, the enrollment will be paused. The remaining 15 subjects for each cohort will be enrolled only after the review by the DMC of the safety results obtained through Day 14 has been finalized (Table 2). In addition, enrollment of the first 5 subjects of the next cohort will only proceed after the Day 14 safety results of the first 5 subjects of the previous cohort have been reviewed by the

DMC. Furthermore, all available Day 14 and Day 29 safety results will be included in DMC review between the different enrollment stages.

Table 2. Overview of staggered entry of subjects based on DMC reviews

Stage	Dosage Cohort	MenC-CRM ₁₉₇ / Aluminium Hydroxide (n)	MenC-CRM ₁₉₇ / Aluminium Hydroxide /LHD153R (n)
1	1	1	4
Enrollment pause until DMC review of Stage 1 Day 14 Safety Results			
2	1	3	12
	2	1	4
Enrollment pause until DMC review of Stage 1 Day 29 and Stage 2 Day 14 Safety Results			
3	2	3	12
	3	1	4
Enrollment pause until DMC review of Stage 2 Day 29 and Stage 3 Day 14 Safety Results			
4	3	3	12
	4	1	4
Enrollment pause until DMC review of Stage 3 Day 29 and Stage 4 Day 14 Safety Results			
5	4	3	12

Tables 3 and 4 display the time and events until Day 29 and Day 366 respectively. Sections referred to in these tables are those in the protocol.

Table 3. Times and Events Table (until Day 29)

	Visit Type	Clinic Visit	Clinic Visit	Clinic Visit	Clinic Visit	Clinic Visit	Phone Call	Clinic Visit
	Study Day	-28 to -3	1	4	8	15	22	29
	Visit Window (Days)	n/a	n/a	n/a	-1/+1	+1	n/a	-2/+2
	Visit Number	Screening	1	2	3	4	5	6
Study Event	Protocol References							
Study Treatment								
Vaccination	Section 5.2		X					
Screening and Safety								
Informed Consent	Section 5.1.1	X						
Demographic Data & Medical History	Sections 5.1.2	X						
Physical Exam	Sections 5.1.2 and 5.2.1	X	X _a					
Safety Laboratory blood draw (10 mL)	Section 7.1.7	X	X _b		X			X
Urinalysis	Sections 7.1.7	X	X _b		X			X
Pregnancy Test	Sections 5.1.2 and 5.2.1	X	X _a					

19 JAN 16 Final Version 1.0

Confidential

Page 13 of 59

Exclusion/Inclusion Criteria	Section 4.0	X	X _a					
Randomization	Section 5.2.3		X _a					
30 min and 24 hr Post Injection Assessment	Section 5.2.5		X _c					
Subject Diary Dispensed with Training	Section 5.2.5		X					
Subject Diary Reminder	Section 5.2.5			X	X			
Subject Diary Reviewed and Collected	Section 5.3.1					X		
Assess all solicited AEs	Section 7.1.1 and 7.1.3					X		
Assess all unsolicited AEs	Sections 7.1.2 and 7.1.3	X	X	X	X	X		

BCDM-14 TEMP 01 / Atlas No. 296412

	Visit Type	Clinic Visit	Clinic Visit	Clinic Visit	Clinic Visit	Clinic Visit	Phone Call	Clinic Visit
Assess SAEs	Section 7.1.4	X	X	X	X	X	X	X
Assess AESIs	Section 7.1.4.1	X	X	X	X	X	X	X
Assess NOCDs, medically attended AEs, AEs leading to withdrawal	Sections 7.1.3	X	X	X	X	X	X	X
Assess relevant medications	Sections 5.1.2 and 6.5	X	X	X	X	X	X	X
Blood draws for Immunogenicity and Exploratory Objectives								
Serum Blood Draws (Primary/Secondary Objectives; 10 mL)	Section 3.5		X _a		X			X

Version No. 5 / Version Date: April 30, 2015

19 JAN 16 Final Version 1.0

Confidential

Page 14 of 59

Serum Blood Draws (Exploratory Objectives; 5 mL)	Section 3.5		X _d	X	X			
Whole Blood Draws (Exploratory Objectives; 3 mL)	Section 3.5		X _e	X				
Whole Blood Draws (Exploratory Objectives; 5 mL)	Section 3.5		X _f	X	X			
Whole Blood Draws (Exploratory Objectives; 20 mL)	Section 3.5		X _g	X				
Whole Blood Draws (Exploratory Objectives; 50 mL)	Section 3.5							X
Whole Blood Draws (Exploratory Objectives; 70 mL)	Section 3.5		X _a		X			

Notes:

^a

Procedure must be performed prior to vaccination.

^b Two blood draws (2 x 10 mL) and two urine samples must be taken at Study Day 1, i.e. at baseline (prior to vaccination) and at 24 h after vaccination.^c

4. RANDOMIZATION AND BLINDING

4.1 Method of Group Assignment and Randomization

Subjects will be randomized in a 1:4 ratio to receive a single intramuscular (IM) vaccination of either the licensed aluminium hydroxide adjuvanted Meningococcal CCRM197 Conjugate Vaccine (Menjugate®) or the investigational vaccine, MenCCRM197/Aluminium Hydroxide/LHD153R. Each of the four cohorts will evaluate a different dosage of LHD153R.

For further details, refer to [section 5.2.3](#) of the protocol.

4.1.1 Definition of Vaccination Errors

A vaccine administration error occurs when a subject receives a dose of study vaccine that was not reconstituted as instructed or administered by a different route from the intended route of administration.

An overdose of study vaccine occurs when a dosage higher than the recommended dosage is administered in one dose.

The list below provides some examples of potential errors that may occur during vaccination:

- Subjects got vaccinated with a vaccine different from the one assigned at randomization
- Subjects got vaccinated with the correct vaccine but containing a lower volume

See [section 7](#) of this document for a complete guidance on how vaccination errors are handled in the statistical analysis.

4.1.2 Forced Randomization

Not applicable.

4.2 Blinding and Unblinding

For details, refer to [section 3.3](#) of the protocol.

The unblinding of a subject during the study is reported as a major protocol deviation, except for Pharmacovigilance unblinded suspected unexpected serious adverse reactions (SUSAR). The unblinding will be documented.

The first-line analysis excludes unblinded subject(s) in immunogenicity statistical analyses based on the per-protocol set (PPS). The unblinded subjects will be included in the full analysis set (FAS) and safety sets.

As described in section 3 of PXL SOP-EP.CL-WW-003-01 ('Administration of Investigational Product'), these two steps are taken to ensure blindness in observerblinded studies except in cases where the protocol stipulates otherwise:

- The Principal Investigator, Investigator, Registered Nurse, Licensed Practical Nurse, Pharmacist or other licensed health care provider who assists in the IP preparation will not perform other procedures on that study;
- An independent Principal Investigator, Investigator, Registered Nurse, Licensed Practical Nurse, Pharmacist or other licensed health care provider who performs the dispensing procedures and has therefore been unblinded will not perform any dosing procedures nor will they participate in any assessment procedure or the execution of the study in any other way.

5. SAMPLE SIZE AND POWER CONSIDERATIONS

For details, refer to [section 8.5](#) of the protocol.

Sample size/power considerations are included in the study protocol. Technical details including statistical assumptions and software are given in a separate sample size memo authored by the study Biostatistician. In the same document, a statistical co-reviewer verified and documented the sample size/power considerations. This document was completed prior to finalization of the protocol and stored in Home/analysis/v132/v132_01exp/sample_size/dev/docs.

6. DETERMINATION OF PROTOCOL DEVIATIONS

6.1 Definition of Protocol Deviations

Major (Clinical Study Report (CSR) reportable) protocol deviations (PDs) are defined in accordance with ICH E3 as important PDs related to study inclusion or exclusion criteria, conduct of the trial, subject management or subject assessment resulting in the potential to jeopardize the safety or rights of the trial subjects or the scientific value of the trial.

All reportable PDs will be evaluated before unblinding and classified according to ICH into the following five categories:

- Subject developed withdrawal criteria during the study but was not withdrawn:
 - Underlying medical condition forbidden by the protocol or which may influence immune response.
 - Subject received wrong vaccine or incorrect dose.
 - Study vaccine was not administered at all.
 - Vaccine administration not according to protocol.
 - Randomization failure.
- Subject took an excluded concomitant medication:
 - Administration of concomitant vaccine(s) forbidden in the protocol.
 - Administration of any medication forbidden by the protocol.
- Subject randomized and did not satisfy the entry criteria:
 - Subject did not meet entry criteria.
- Deviations from key study procedures:
 - Randomization code was broken.
 - Subject did not provide any post-vaccination safety data.
 - Subject did not comply with blood draw schedule.
 - Serological results not available post-vaccination.
 - Obvious incoherence, abnormal serology evolution or error in data.

Major (CSR reportable) PD will lead to exclusion of the subject or part of the subject's data from at least one analysis set.

The number of subjects in any and by PD category will be summarized by dosage and overall and individual subject listings will be provided in an appendix.

Prior to unblinding, designated PXL and Sponsor staff will develop a memo that describes the PDs that lead to exclusions from analysis sets. This memo will be signed off by at least the Biostatistician and the Cluster Physician and will be included in the trial master file.

Prematurely terminating study participation for reasons such as withdrawal of consent or occurrence of adverse events (including death) is not considered as a PD. The missing assessments that should have otherwise been collected for that subject later in the study are also not considered as a PD.

6.2 Determination of Protocol Deviations

Prior to unblinding, a set of listings will be provided to the Cluster Physician and the Clinical Trial Leader (CTL) for review according to PXL SOP-EP.BS-WW-008-01.

The listings will be programmed following the list presented in table in section 7.3.8, and specifically using the PD codes specified in the first column. In addition, PDs will be evaluated during periodic review meetings as described in the Protocol Deviations Manual.

6.3 Exclusions of Individual Values for Safety Analysis

Some local and systemic adverse events will be directly measured by the subject and will not be subject to a reconciliation process, even if they are biologically implausible. Therefore these implausible measurements will be included in listings but excluded from summary tables. Implausible measurements are summarized in Table 6.3-1:

Table 6.3-1. Implausible Solicited Adverse Events

Parameter	Implausible measurements
Body temperature	<=33°C or >=42°C
Erythema	> 900 mm or <0 mm
Induration	> 500 mm or <0 mm
Swelling	>500 mm or < 0 mm

7. ANALYSIS SETS

7.1 All Enrolled Set

All screened subjects who provide informed consent and provide demographic and/or other baseline screening measurements, regardless of the subject's randomization and vaccination status in the trial, and receive a subject ID.

Demography and baseline characteristics tables as well as subject listings will be produced on the All Enrolled Set.

7.2 All Exposed Set

All subjects in the All Enrolled Set who receive a study vaccination.

7.3 Safety Set

Solicited Safety Set

All subjects in the All Exposed Set who:

- Provide post vaccination local or systemic solicited adverse event data. Unsolicited Safety Set

All subjects in the All Exposed Set who:

- Have post-vaccination unsolicited adverse event data.

Overall Safety Set

All subjects who are in the solicited safety set and/or in the unsolicited safety set.

Subjects providing only 30 minutes postvaccination safety data will be reported separately in a 30 minute postvaccination safety analysis and excluded from all other safety analysis.

In case of vaccination error, subjects will be analyzed as "treated" (i.e., according to the vaccine a subject receives, rather than the vaccine to which the subject is randomized).

If a subject is unblinded during the study, he/she will be included in all safety sets.

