7.7 Overview of Analysis Sets by PD Code

Table mock-ups with summaries of the number of available subjects by objective and analysis set are given below.

Table 7.7-1: Safety Sets

PD code	PD Description	All Exposed Set	Overall Safety Set	Unsolicited Safety Set	Solicited Safety Set			
					T30m	D1-D4*	D5-D8	D8-D14
	Exclusion code	EXPFL	SAFFL	SSU10FL	SSS01FL	SSS02FL	SSS03FL	SSS04FL
100	Study vaccine not administered AT ALL	EXC	EXC	EXC	EXC	EXC	EXC	EXC
115	Subject did not provide any post-vaccination unsolicited safety data	None	None	EXC	None	None	None	None
116	Subject did not provide any post-vaccination solicited safety data	None	None	None	EXC	EXC	EXC	EXC

EXC = excluded from this analysis set.

* Without 30 minutes post-vaccination.

All Safety sets and codes correspond to the primary safety objective.

Table 7.7-2: Immunogenicity Sets

PD code	PD Description	PPS	FAS-2		FAS-1			
			D1	D29	D1	D8	D29	D181
	Exclusion code	PPS01FL	FAS01FL	FAS02FL	FAS03FL	FAS04FL	FAS05FL	FAS06FL
100	Study vaccine not administered AT ALL	EXC						
110	Serological results are not available	EXC						
110.1	Serological results are not available for hSBA	EXC						
110.2	Serological results are not available for ELISA	EXC	None	None	EXC	EXC	EXC	EXC
112	Obvious deviation from Laboratory Manual or error in laboratory data	EXC						
112.1	Incoherence between CRF and CLS database in terms of sample availability (e.g. sample not collected but result is available)	EXC						
112.2	Label error of blood samples that could not be resolved	EXC						
112.3	Wrong handling of laboratory samples with impact on the results (e.g. critical deviations during storage at sites or shipment but sample was tested)	EXC						

19 JAN 16 Final Version 1.0

Confidential

Page 26 of 59

120	Randomization failure	EXC	EXC	EXC	EXC	EXC	EXC	EXC
120.1	Subject randomized to the wrong strata	EXC	None	None	None	None	None	None

BCDM-14 TEMP 01 / Atlas No. 296412

PD code	PD Description	PPS	FAS-2		FAS-1			
			D1	D29	D1	D8	D29	D181
	Exclusion code	PPS01FL	FAS01FL	FAS02FL	FAS03FL	FAS04FL	FAS05FL	FAS06FL
120.2	Subject received another vaccine than allocated (Actual Arm different from Planned Arm)	EXC	None	None	None	None	None	None
130	Randomization code was broken	EXC	None	None	None	None	None	None
140	Vaccination not according to protocol	EXC	None	None	None	None	None	None
140.1	Administration of temperaturedeviated vaccine	EXC	None	None	None	None	None	None

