8.2.1 Safety Data

To minimize the effect of dropouts and missing data, the study period will be divided into time intervals for statistical analysis of safety.

Unsolicited adverse events: these events will be reported from the date of signed informed consent to Day 14 and from Day 15 to study termination (for SAEs, Medically Attended AEs, NOCDs and AESIs).

Solicited adverse events, the solicited study period (Days 1-14) after vaccination will be divided into these intervals: 30 min, Days 1-4 (without 30 min), Days 5-8, Days 1-8 (without 30 min), Days 8-14 and Days 1-14 (without 30 min).

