13.2 Solicited Local and Systemic Adverse Events

For details, refer to [section 7.1.1](#) of the protocol.

Plausible observations are those with non-missing values other than those “Not done/unknown” or implausible values (see [section 6.3](#)). Implausible measurements will be excluded from summary tables but included in listings.

Solicited adverse events will be recorded at 30 minutes and Day 1 directly into the clinical database; and, from Day 2 to Day 14 in the subject diaries.

The analyses of solicited adverse events will be performed separately at these intervals: 30 minutes, Days 1-4 (without 30 minutes), Days 5-8, Days 8-14, Days 1-8 (without 30 minutes) and Days 1-14 (without 30 minutes). In addition, solicited AEs ongoing after day 14 will be presented as unsolicited AEs.

In the case of local AEs, for grades 1 to 3 (i.e., Mild to Severe), refer to Appendix A in the protocol. Grade 4 (Potentially Life Threatening) will be defined as follows (see also Appendix 2):

- Pain: Emergency room (ER) visit or hospitalization.
- Tenderness: ER visit or hospitalization.
- Erythema/Redness: Necrosis or exfoliative dermatitis.
- Induration/Swelling: Necrosis.

(Guidance for Industry Toxicity Grading Scale for Healthy Adult and Adolescent Volunteers Enrolled in Preventive Vaccine Clinical Trials, USDA, 2007).

All summary tables will include the number and percent of subjects with solicited adverse events by dosage group and time interval as well as overall.

Summary tables of solicited adverse events by severity and maximal severity will be created. Summary tables showing the occurrence of any local or systemic solicited adverse event will also be created.

The solicited local adverse events include these evaluations at the injection site: erythema, induration, swelling and pain. For erythema, induration and swelling recorded originally as diameters (mm), these categories will be used to summarize the data: None (0 mm), Grade 0 (<25 mm), Any (\geq 25 mm) with subcategories for Mild (25-50 mm), Moderate (51-100 mm) and Severe ($>$ 100 mm).

In the case of systemic AEs, for grades 1 to 3 (i.e., Mild to Severe), refer to Appendix B in the protocol. Grade 4 (Potentially Life Threatening) will be defined as follows (see also Appendix 3):

- Fever: >40 C (>104 F)
- Chills: ER visit or hospitalization
- Loss of Appetite: ER visit or hospitalization
- Nausea: ER visit or hospitalization for hypotensive shock

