- Vomiting: ER visit or hospitalization for hypotensive shock
- Diarrhea: ER visit or hospitalization
- Generalized Myalgia: ER visit or hospitalization
- Generalized Arthralgia: ER visit or hospitalization
- Headache: ER visit or hospitalization,
- Fatigue: ER visit or hospitalization,
- Generalized Rash, ER visit or hospitalization Urticaria: ER visit or hospitalization.

Body temperature will be broken down by route of measurement according to the recommendations of the Brighton collaboration and will be summarized according to the 3 schemes described below:

- by 0.5 °C increments: <36.0 , ≥ 36.0 - <36.5 , ≥ 36.5 - <37.0 , ≥ 37.0 - <37.5 , ≥ 37.5 - <38.0 , ≥ 38.0 - <38.5 , ≥ 38.5 - <39.0 , ≥ 39.0 - <39.5 , ≥ 39.5 - <40.0 , ≥ 40.0 °C
- by 1.0 °C increments: <36.0 , ≥ 36.0 - <37.0 , ≥ 37.0 - <38.0 , ≥ 38.0 - <39.0 , ≥ 39.0 - <40 , ≥ 40 °C

- $<38.0, \geq 38.0$ °C

Fever, defined as a body temperature of ≥ 38 °C irrespective of route of measurement, will be considered a systemic adverse event.

The analyses will encompass summaries of the data on five levels:

1. Daily reports of subjects with solicited adverse events.
2. Time of first onset of solicited adverse events (excluding 30 min post-vaccination).
3. Solicited adverse events, maximum event severity by event and time interval.
4. Number of days with solicited adverse events.
5. Solicited adverse events and indicators of solicited adverse events, occurrence of at least one event by category (local, systemic) and time interval.

For each of the time intervals presented in the summaries, only subjects with at least one plausible observation for the solicited adverse events will be included.

Level 1: Daily reports of solicited adverse event

For each time interval, only subjects with at least one plausible observation for the solicited adverse event will be included in the analysis. For each time interval, the number and percent of subjects will be presented by dosage group, solicited adverse event and overall.

Level 2: Time of first onset of solicited adverse events

The **time of first onset** of a solicited adverse event experienced by each subject is the time point at which the event first occurred. For erythema, induration and swelling, a threshold of ≥ 25 mm will be used. The summary will provide the frequencies and percentages of subjects with first onset of each solicited adverse events by dosage group and time point.

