For each dosage group, the first onset of the adverse event will be used for each subject.

Level 3: Solicited adverse events, maximum event severity by event and interval

The **maximum event severity** will be defined if there is at least one plausible observation within the time interval. Each subject's data will be aggregated across the time intervals and summarized according to the maximal severity observed for each adverse event,

followed by a summary across subjects for each dosage group. Subjects without any solicited adverse event data in the interval will be excluded from the analysis.

Level 4: Number of days with solicited adverse events

The number of days with the adverse event is defined irrespective of severity. This means at least ‘mild’ solicited adverse event that are assessed qualitatively and ≥ 25 mm for erythema, induration and swelling. If a solicited adverse event continues beyond day 14 the period after day 14 is added.

The frequency distribution of the number of days will be provided in a summary table by dosage group and adverse event.

Level 5: Solicited adverse events, occurrence of at least one event by category (local, systemic) and interval.

The **occurrence of at least one solicited adverse event** is defined as “any” for a subject who reports greater than “Grade 0” (≥ 25 mm for erythema, swelling and induration) for the respective event and “Grade 0” otherwise. The occurrence of at least one solicited adverse event (i.e., none versus any) will be summarized by category (i.e., local, systemic, any), by dosage group, and by time interval.

Medications to treat or prevent pain or fever will be summarized by frequencies and percentages of subjects reporting use of the medications by interval: 30 min, Days 1-4 (without 30 min), Days 5-8, Days 1-8 (without 30 min), Day 8-14, Days 1-14 (without 30 min).

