13.3 Unsolicited Adverse Events

All the unsolicited adverse events occurring during the study, judged either as probably related, possibly related, or not related to vaccination by the investigator, will be recorded.

The original verbatim terms used by investigators to identify adverse events in the Case Report Forms (CRFs) will be mapped to preferred terms using the MedDRA dictionary. The unsolicited adverse events will then be grouped by MedDRA preferred terms into frequency tables according to system organ class. All reported adverse events, as well as adverse events judged by the investigator as at least possibly related to study vaccine, will be summarized by dosage group, according to system organ class and preferred term within system organ class. When an unsolicited adverse event occurs more than once for a subject, the maximal severity and strongest relationship to the dosage group will be counted.

Only treatment-emergent adverse events will be analyzed, i.e., excluding those after a subject has given informed consent but before vaccination. The selection of unsolicited adverse events and the assignment to time intervals (Days 1-14 after vaccination, and from Day 15 post vaccination until study termination) will be done by day of onset and not by days ongoing/persisting.

The analysis of unsolicited adverse events comprises the following categories:

- Any unsolicited adverse event.
- Possibly or probably related unsolicited adverse events.
- Unsolicited adverse events leading to death.
- Serious adverse events.
- Possibly or probably related serious adverse event.
- Unsolicited adverse events leading to premature withdrawal from study.
- Medically attended adverse events.
- Adverse events of special interest (AESI).
- New onset of chronic disease (NOCD).

Data listings of all adverse events will be provided by subject. In addition, adverse events in the categories above will be provided as listed data.

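### Section 7.3 drops subjects with only 30-minute data from the death, SAE, AESI and withdrawal tables, and separately no cumulative solicited table includes a reaction seen only at 30 minutes

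*SAP*

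**What the plan says.** Section 7.3 (Safety Set) builds the Overall Safety Set from subjects in the solicited set, the unsolicited set, or both. It then adds: "Subjects providing only 30 minutes postvaccination safety data will be reported separately in a 30 minute postvaccination safety analysis and excluded from all other" (meaning every other analysis of safety). No category of event is exempted.

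Section 8.2.1 gives the solicited intervals as "30 min, Days 1-4 (without 30 min), Days 5-8, Days 1-8 (without 30 min), Days 8-14 and Days 1-14 (without 30 min"). Section 13.2 repeats them, ending with "Days 1-8 (without 30 minutes) and Days 1-14 (without 30 minutes"). The summary levels in 13.2 that matter here are:

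- Level 2: "Time of first onset of solicited adverse events (excluding 30 min post-vaccination").
- Level 3: maximum severity of each event, by time interval.
- Level 5: occurrence of at least one event, which "will be summarized by category (i.e., local, systemic, any), by dosage group, and by time interval".

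Section 13.3 lists the unsolicited categories. They include deaths, serious events, related events, AESIs and "Unsolicited adverse events leading to premature withdrawal from study". Events are assigned to Days 1-14 or to Day 15 onwards by day of onset, and the first 30 minutes are not set apart.

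**The concern.** There are two mechanisms, and they should be kept apart.

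**Exclusion of subjects (7.3).** A subject may have nothing beyond the 30-minute record because of what happened in those 30 minutes. If so, the exclusion depends on outcome. Both the event and the subject leave the tables in which a reader would look for deaths, serious events and withdrawals due to adverse events.

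**Exclusion of the reading (8.2.1 and 13.2).** A solicited reaction present at 30 minutes and gone by the next reading is counted only in the 30-minute column, even if the subject completes follow-up. No planned solicited table gives the proportion with any reaction, or the maximum severity, from vaccination to Day 14.

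Safety is a primary objective (section 2.1). The Day 29 interim analysis serves selection of the adjuvant dosage, and its safety tables to Day 29 are final (section 14.1). With 16 subjects per group, one subject is visible in any of these tables.

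**Working it through.** The SAP states no figure on this point that could be reproduced. The check sets the rules side by side and then sizes one case.

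**Inputs**
- Group size: 16 in each LHD153R group, and 4 × 4 = 16 in the MenC group over the four cohorts (Table 1).
- Interval method: exact Clopper-Pearson 95%, which the SAP uses for immunogenicity percentages.
- Assumption: one subject in a group has an immediate event. The SAP gives no expected frequency.

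**Step 1. What the 7.3 exclusion adds.** Section 13.2 already limits each solicited interval to subjects with at least one plausible observation in it. A subject with only 30-minute data therefore drops out of the later solicited intervals without help from 7.3. The sentence in 7.3 does its extra work mainly in the unsolicited tables of 13.3 and the combined summary of 13.4.

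**Step 2. Size of the 7.3 exclusion.** The subject leaves the numerator and the denominator.
- Kept: 1/16 = 6.3%. The lower limit is 1 − 0.975^(1/16) = 0.2% and the upper limit is the 97.5% point of Beta(2, 15) = 30.2%.
- Dropped: 0/15 = 0%. The upper limit is 1 − 0.025^(1/15) = 21.8%.
- Range: with no such subject nothing changes. With two in one group, 2/16 = 12.5% (1.6% to 38.3%) becomes 0/14 = 0% (0% to 23.2%).

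**Step 3. Size of the interval rule.** A subject with full follow-up and a reaction only at 30 minutes stays in the denominator.
- Reading included: 1/16 = 6.3% (0.2% to 30.2%).
- Days 1-14 without 30 minutes: 0/16 = 0%, upper limit 1 − 0.025^(1/16) = 20.6%.

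**Step 4. Whether the total can be recovered from the two columns.** Let a be the number with the event at 30 minutes and b the number on Days 1-14 without 30 minutes. In a group of n with both readings, the total lies between max(a, b) and min(a + b, n). With a = b = 1 and n = 16, it is either 1/16 = 6.3% or 2/16 = 12.5%. The overlap is not tabulated, so the summary tables do not settle which. The by-subject listings would.

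**Step 5. Which tables each mechanism reaches.**

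| Table | Only 30-minute data | Reaction only at 30 min, later data present |
|---|---|---|
| 30-minute analysis | shown | shown |
| Listings | shown | shown |
| Disposition, if withdrawn | shown | not applicable |
| Levels 2, 3, 5 beyond 30 min | absent | absent |
| Unsolicited events, SAEs, AESIs, withdrawals (13.3) | absent | unaffected |
| Combined summary (13.4) | absent | may be included, not split by severity |

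**The case against.** The strongest reply is that nothing is lost. Thirty minutes is a planned interval, section 7.3 promises a separate analysis, all adverse events are listed by subject, and a withdrawal appears in disposition by main reason. All of this stands, and it limits the consequence. The omission is from particular summary tables and not from the report.

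Second, the 7.3 case is narrow. Temperature is taken repeatedly up to 24 hours, a safety blood draw follows at 24 hours, and Day 1 solicited events go directly into the database, so a lost diary does not create the case. One can also argue that a subject with a recorded serious event has unsolicited data and is not a 30-minute-only subject. That is a fair reading. However, 7.3 does not say so, and an event whose whole record falls within the first 30 minutes fits its wording.

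Third, dividing the period into intervals is deliberate, to limit the effect of dropout (8.2.1). That justifies the separate columns. It does not require that no cumulative column contain the first reading.

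Some stronger readings are tempting but not supported:

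- **That immediate reactions in general vanish from the SAE and withdrawal tables.** Section 13.3 assigns by day of onset, so a subject with any later data keeps an immediate serious or unsolicited event in Days 1-14.
- **That Table 7.7-1 clearly contradicts 7.3.** The table lists deviation codes such as "Subject did not provide any post-vaccination unsolicited safety data". Section 6.1 does not count premature termination as a deviation, so a missing code proves little. At most this is a minor point to reconcile.
- **That Level 4 is affected.** It counts days with an event and states neither an interval split nor a 30-minute exclusion.
- **That dose escalation would rest on incomplete data.** Nothing in sections 3 or 15 limits the DMC to tables without 30 minutes.

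**Conclusion.** Both points hold, within limits.

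The 7.3 rule, followed as written, can remove an exposed subject with an immediate serious event from the death, SAE, AESI, related-event and withdrawal tables. It is probably rare and depends on a subject having no safety data after 30 minutes. For one such subject, 1/16 (6.3%) becomes 0/15. The event remains in the 30-minute analysis and the listings, and a withdrawal remains in disposition.

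The interval rule needs no loss to follow-up. A solicited reaction confined to the 30-minute reading is missing from Levels 2, 3 and 5 beyond that column, and 1/16 becomes 0/16. The summary tables then give no any-reaction or maximum-severity incidence from vaccination to Day 14. SAE and unsolicited-event reporting for that subject is untouched.

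The sizes are illustrations resting on one affected subject in a group. This is worth changing because a stated rule can exclude subjects according to outcome on a primary safety objective, and the correction is nearly free.

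**What to change.** 1. In section 7.3, limit the exclusion of subjects with only 30-minute data to the solicited intervals after 30 minutes. State that they stay in the Overall and Unsolicited Safety Sets for unsolicited events, deaths, SAEs, AESIs, related events and adverse events leading to withdrawal.
2. In sections 8.2.1 and 13.2, add an interval from vaccination through Day 14 including 30 minutes to Level 3 and Level 5. Keep all present intervals beside it.

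The cost is a change of SAP wording and one extra column in two table types. The drawback is that a few subjects with very short follow-up enter these denominators. Those without an early event would count as event-free to Day 14. A footnote giving their number per group deals with this.
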